Type of Visit	Clinic	Clinic	Clinic	Clinic	Hospital	Phone Call	Clinic	Clinic		
Assess acute reactions for at least 30 minutes after study intervention administration	X	X								
Provide/ensure participant has a thermometer and measuring device	X	X								
Review reactogenicity e-diary data (daily review is optimal during the active diary period of 7 days following study intervention administration)	↔	↔								
Review ongoing reactogenicity e-diary symptoms with participant and obtain stop dates		X	X							
Record pregnancy outcome information					X	X				
Record AEs and SAEs as appropriate ^f	X	X	X	X	X ^d	X	X ^d	X ^d	X ^d	X ^d
Collect e-diary or assist the participant to delete application								X		

Visit Number (Maternal Participants)	1	2	3	4	5	6	7	8	Unplanned	Unplanned
Visit Description	Screening: -28 Days to Vaccination 1	Vaccination 2	2-Week Post-Vaccination 2 Follow-up ^a	1-Month Post-Vaccination 2 Follow-up ^a	Delivery	1-Week Postdelivery Follow-up Call	1-Month Postdelivery Follow-up ^b	6-Month Postdelivery Follow-up For Participants Originally Randomized to Receive BNT162b2	Potential COVID-19 Illness Visit ^c	Potential COVID-19 Convalescent Visit
Visit Window (Days)	Day 1 Visit 1	19 to 23 Days After Visit 1	11 to 17 Days After Visit 2	28 to 35 Days After Visit 2	Varies	7 to 10 Days After Delivery	21 to 35 Days After Delivery	160 to 200 Days After Delivery	Optimally Within 3 Days After Potential COVID-19 Illness Onset	28 to 35 Days After Potential COVID-19 Illness Visit
Type of Visit	Clinic	Clinic	Clinic	Clinic	Hospital	Phone Call	Clinic	Clinic		
Collection of COVID-19-related clinical and laboratory information (including local diagnosis)									X	X

Abbreviations: EDD = estimated delivery date; HIV = human immunodeficiency virus; LMP = last menstrual period.

- The 2-week postvaccination follow-up and 1-month postvaccination follow-up visits will not be performed if delivery occurs before the visits. If delivery occurs before Vaccination 2, the second dose should be given as soon as possible after delivery. Once delivery occurs, the visit windows are calculated based on the delivery date.
- All maternal participants will be unblinded. Placebo recipients will be given BNT162b2 and move to follow the procedures in [Section 1.3.2](#).
- The COVID-19 illness visit may be conducted as an in-person or telehealth visit.
- Only AEs occurring up to 48 hours after each blood draw and nasal midturbinate swab collection must be recorded.

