8.11.1.2. Visit 3 – 2-Week Postvaccination Follow-up (Clinic)

If delivery occurs before this visit, this visit will not be conducted.

- Phase 3 only: For participants who are HIV-infected, record HIV viral load and CD4 count results from the most recent test performed since their last visit (if any).
- Record nonstudy vaccinations as described in [Section 6.5](#).
- Collect and record concomitant medication associated with AE/SAEs.
- Review the participant's reactogenicity e-diary data. Collect stop dates of any reactogenicity e-diary events ongoing on the last day that the reactogenicity e-diary was completed and record stop dates in the CRF if required.
- Ensure and document that the participant is still eligible for continued participation.
- Collect a blood sample (approximately 20 mL) for immunogenicity testing.
- Record AEs and SAEs as described in [Section 8.3](#).
- Ask the participant to contact the site staff or investigator if an emergency room visit or hospitalization occurs.
- Ask the participant to contact the site staff or investigator if the participant experiences acute chest pain, shortness of breath, or palpitations (see [Section 8.14](#)).
- Ask the participant to contact the site staff or investigator (this could be via the COVID-19 illness e-diary) immediately if she experiences any COVID-19 illness symptoms as detailed in [Section 8.13](#).
- Schedule an appointment for the participant to return for the next study visit.
- Complete the source documents.
- The investigator or an authorized designee completes the CRFs.

8.11.1.3. Visit 4 – 1-Month Postvaccination Follow-up Visit (Clinic: 28-35 Days After Visit 2)

If delivery occurs before this visit, this visit will not be conducted.

- Phase 3 only: For participants who are HIV-infected, record HIV viral load and CD4 count results from the most recent test performed since their last visit (if any).
- Measure vital signs (body temperature, pulse rate, and seated blood pressure).

- Perform targeted physical examination evaluating/noting any clinically significant abnormalities within the following body systems: general appearance; skin; head, eyes, ears, nose, and throat; heart; lungs; abdomen; musculoskeletal; extremities; neurological; and lymph nodes. Significant medical and surgical history and abnormal observations from the physical examination will be documented and recorded in the CRF.

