Redness	>2.0 cm to 5.0 cm (5 to 10 measuring device units).	>5.0 cm to 10.0 cm (11 to 20 measuring device units).	>10 cm (≥21 measuring device units).	Necrosis or exfoliative dermatitis.
Swelling	>2.0 cm to 5.0 cm (5 to 10 measuring device units).	>5.0 cm to 10.0 cm (11 to 20 measuring device units).	>10 cm (≥21 measuring device units).	Necrosis.

For each local reaction reported for each dose, the maximum severity grade will be derived for the e-diary collection period (Day 1 through Day 7, where Day 1 is the day of each dose) as follows:

maximum severity grade = highest grade (maximum severity) within 7 days after vaccination (Day 1 through Day 7) among severity grades where the answers are neither “no” nor missing for at least 1 day during the interval from Day 1 through Day 7.

Duration (First to Last Day Reported)

For participants experiencing any local reactions (or those with a derived reaction as described in [Table 4](#)), the maximum duration (last day of reaction – first day of reaction + 1) will be derived for each study vaccination. Resolution of the reaction is the last day on which the reaction is recorded in the e-diary or the date the reaction ends if it is unresolved during the participant e-diary recording period (end date collected on the CRF), unless chronicity is established. If there is no known end date, the duration will be considered unknown and set to missing. However, if a reaction is ongoing at the time of a subsequent vaccination, the end date/day for the ongoing reaction would be the date/day that the next vaccine is administered, which will be used for the duration computation. Participants with no reported reaction have no duration.

Onset Day

The onset day of each local reaction will be derived. Onset day is defined as the first day after vaccination that a reaction is reported of any severity.

For the onset day of each local reaction, if participants report a change in severity of the local reaction, only the first day of reporting that specific local reaction will be counted.

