3.1.1.2. Systemic Events (Systemic Event Symptoms and Fever)

The systemic events assessed and recorded in the e-diary are fever, vomiting, diarrhea, headache, fatigue/tiredness, chills, new or worsened muscle pain, and new or worsened joint pain from Day 1 through Day 7, where Day 1 is the day of each dose. The derivations for systemic events will be handled in a way similar to the handling of local reactions with respect to presence of event, severity level, duration, and onset day (see [Section 3.1.1.1](#)).

The symptoms will be assessed by the participant as absent, mild, moderate, or severe according to the grading scale in [Table 5](#).

Table 5. Systemic Event Grading Scale

	Mild (Grade 1)	Moderate (Grade 2)	Severe (Grade 3)	Potentially Life Threatening (Grade 4)
Vomiting	1-2 times in 24 hours.	>2 times in 24 hours.	Requires IV hydration.	Emergency room visit or hospitalization for hypotensive shock.
Diarrhea	2 to 3 loose stools in 24 hours.	4 to 5 loose stools in 24 hours.	6 or more loose stools in 24 hours.	Emergency room visit or hospitalization for severe diarrhea.
Headache	Does not interfere with activity.	Some interference with activity.	Prevents daily routine activity.	Emergency room visit or hospitalization for severe headache.
Fatigue/tiredness	Does not interfere with activity.	Some interference with activity.	Prevents daily routine activity.	Emergency room visit or hospitalization for severe fatigue.
Chills	Does not interfere with activity.	Some interference with activity.	Prevents daily routine activity.	Emergency room visit or hospitalization for severe chills.
New or worsened muscle pain	Does not interfere with activity.	Some interference with activity.	Prevents daily routine activity.	Emergency room visit or hospitalization for severe new or worsened muscle pain.
New or worsened joint pain	Does not interfere with activity.	Some interference with activity.	Prevents daily routine activity.	Emergency room visit or hospitalization for severe new or worsened joint pain.

Abbreviation: IV = intravenous.

Oral temperature will be collected in the evening, daily, for 7 days following each dose (Days 1 through 7, where Day 1 is the day of each dose) and at any time during the 7 days that fever is suspected. Fever is defined as an oral temperature of $\geq 38.0^{\circ}\text{C}$ (100.4°F). The highest temperature for each day will be recorded in the e-diary.

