6.1.1.1.2. Supplementary Analyses

To support the assessment of local reactions, the following endpoints (as defined in [Section 3.1.1.1](#)) will be summarized with the same analysis time point and analysis population as above, and appropriate analysis methodology and reporting results. Confirmed e-diary errors will be excluded from these analyses.

- Duration (days) of each local reaction after each dose.
- Onset day of each local reaction after each dose.

These continuous endpoints will be summarized by displaying n, mean, median, standard deviation, minimum, and maximum for each vaccine group.

In addition, the proportions of participants reporting each prompted local reaction after any dose will be summarized by maximum severity level.

Figures:

Bar charts with the proportions of participants for each local reaction throughout 7 days will be plotted for each vaccine group. The bars will be divided into severity categories to highlight the proportions of participants by maximum severity.

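### Reaction durations without a known end date are dropped, and those running into the next dose are counted as complete, so the supplementary mean and maximum duration can be understated

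*SAP*

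**What the plan says.** SAP 3.1.1.1 defines duration as last day minus first day plus 1. A reaction that resolves within the diary period ends on the last diary day on which it was recorded. One that does not resolve there ends on "the date the reaction ends if it is unresolved during the participant e-diary recording period (end date collected on the CRF), unless chronicity is established".

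Two special cases follow:

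- No end date: "If there is no known end date, the duration will be considered unknown and set to missing".
- Next dose intervenes: "if a reaction is ongoing at the time of a subsequent vaccination, the end date/day for the ongoing reaction would be the date/day" of the next vaccine, and that date is used to compute the duration.

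SAP 3.1.1.2 extends this: "The derivations for systemic events will be handled in a way similar to the handling of local reactions". SAP 3.1.1.3 applies the same rules, where applicable, to antipyretic use. SAP 5.3 adds no other imputation.

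The values feed a supplementary table (SAP 6.1.1.1.2, and similarly 6.1.1.2.2): "Duration (days) of each local reaction after each dose". The statistics are fixed: "These continuous endpoints will be summarized by displaying n, mean, median, standard deviation, minimum, and maximum for each vaccine group".

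On collection, the maternal schedule of activities (protocol 1.3.1) has the line "Review ongoing reactogenicity e-diary symptoms with participant and obtain stop dates", marked at Visits 2 and 3 only. For Visit 3, protocol 8.11.1.2 says: "If delivery occurs before this visit, this visit will not be conducted".

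**The concern.** Under these rules a duration can go missing only if the reaction was unresolved on the last completed diary day and no stop date followed. Whether a value is missing therefore depends on the outcome being summarised. Such a value is not wholly unknown either, because the last day on which the reaction was present is on record. Setting it to missing discards that lower bound. Closing a reaction at the next dose does the reverse: it keeps the lower bound but reports it as a finished duration.

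The doses are not handled alike. A Dose 1 reaction known to be ongoing at Dose 2 is truncated there and stays in the table. After Dose 2 a BNT162b2 recipient has no further study vaccination, so an unresolved reaction with no stop date drops out. Placebo recipients do have a later dose, Vaccination 3 at Visit 101. Read literally, the next-vaccination rule could close their ongoing reactions, and the SAP does not say whether it is meant to.

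What is at stake is a description of tolerability in pregnant women. The mean and maximum could be too low, and comparisons between doses or arms could partly reflect the rule.

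**Working it through.** The documents give no figure for duration, for the share of reactions unresolved at diary end, or for the share without a stop date. There is nothing to reproduce, so what follows gives direction and an illustrative size.

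**1. Which values are affected**

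| Situation | End date used | Effect on duration |
|---|---|---|
| Resolved within the diary | last diary day recorded | complete |
| Outlasts the diary, stop date on CRF | CRF date | complete |
| Outlasts the diary, no stop date | none | missing; lower bound discarded |
| Ongoing at the next vaccination | date of that vaccination | lower bound reported as complete |

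Only the last two rows are at issue. For a Day 1 onset, the Dose 1 cap is the Dose 2 interval plus 1: 20 to 24 days in the 19 to 23 day visit window, and 43 days at the 42-day limit used in SAP section 4 for the evaluable sets.

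**2. Effect on the mean**

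Let u be the share of reactions unresolved at diary end, m the share of those with no end date, S the mean duration of resolved reactions and L that of unresolved ones.

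- True mean = (1 − u)S + uL
- Reported mean = [(1 − u)S + u(1 − m)L] / (1 − um)

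Assume u = 10%, S = 2.5 days and L = 15 days. The true mean is 0.9 × 2.5 + 0.1 × 15 = 3.75 days.

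**3. A value of m tied to the visit schedule**

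The one gap that can be identified in the schedule is a woman who delivers after Dose 2 but before Visit 3 (11 to 17 days after Visit 2). Assume gestational age at entry is uniform and delivery is normal with mean 39.0 to 39.5 weeks and SD 1.5 to 1.8 weeks. Simulation gives 3.7% to 6.1% of women for entry at 24 to 34 weeks, and 5.2% to 8.7% for entry at 27 to 34 weeks. Take m from 4% to 9%, which supposes that every such woman's date is lost and no one else's is.

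- m = 4%: (2.25 + 0.1 × 0.96 × 15) / (1 − 0.004) = 3.69 / 0.996 = 3.70 days, low by 1.2%
- m = 9%: (2.25 + 0.1 × 0.91 × 15) / (1 − 0.009) = 3.615 / 0.991 = 3.65 days, low by 2.7%

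With 175 women per group and the 84.1% injection-site reaction rate that protocol 2.2.1 cites from nonpregnant adults, there are about 147 reactors. The loss is 147 × 0.10 × 0.04 = 0.6 to 147 × 0.10 × 0.09 = 1.3 records per group. Counting also the women who deliver before Dose 2, who lose Visit 3 too, raises the upper end of m to about 10%. The reported mean is then 3.60 / 0.99 = 3.64 days, low by 3.0%.

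**4. Sensitivity to the assumed inputs**

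At m = 10%, with S = 2 or 3 days, L = 10 to 21 days and u = 1% to 10%, the understatement runs from 0.2% to 4.4%. Larger figures need larger m. In the section 2 mixture, m = 50% gives 3.16 days (16% low) and m = 100% gives 2.50 days (33% low). Nothing in the documents points to losses of that size.

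**5. Median and maximum**

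Durations were simulated as geometric with mean 2 or 3 days, with values of 7 days or more treated as unresolved.

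| Share of long durations lost | Median (mean 2 / mean 3) | Expected maximum of 147 (mean 2 / mean 3) |
|---|---|---|
| none | 1 / 2 | 8.5 / 14.2 days |
| 10% | 1 / 2 | 8.4 / 14.0 days |
| 100% | 1 / 2 | 5.9 / 6.0 days |

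The median does not move. The maximum moves materially only under heavy loss.

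**The case against.** The strongest reply is that few stop dates should be missing. Protocol 8.2.2 obliges the site to obtain stop dates for anything ongoing on the last completed diary day, without tying this to a visit. In certain countries field workers continue visits until resolution. Protocol 8.2.2.2 has persisting local reactions reported and entered in the CRF. Protocol 8.12 requires ongoing reactions to be assessed at the next study visit when an unscheduled visit is not held because the woman cannot attend or it is judged unnecessary. Protocol 8.15 requires contact with women who are not completing the diary. So cancelling Visit 3 does not close every route to a date. All of this stands, and it limits the size.

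A reader might infer that the longest reactions drop out as a class. The text does not support that. Reactions that outlast the diary are kept whenever a CRF end date exists, and a woman who stops her diary early with a reaction ongoing may have had a short one. Nor can it be said that Dose 2 reactions will look shorter than Dose 1 reactions: Dose 1 durations can be truncated too, and the net effect is unknown.

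It can also be said that the table prints n, so the shortfall against the number of reactors can be worked out. That is right for missing durations. It does not reveal their lower bounds, and it does not show truncated durations, which are included in n as if complete.

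Finally, duration is supplementary and nothing is tested (SAP 5.1). That stands, and it sets the priority.

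**Conclusion.** The point holds as a minor one. The SAP discards known lower bounds in one case and reports them as complete durations in another, so any resulting bias in the mean and maximum is expected to run downward. Handling may also differ between doses and, depending on how Vaccination 3 is read, between arms.

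The size cannot be determined from the documents. It is zero if every stop date is obtained and no reaction runs into the next dose. It is about 1% to 3% of the mean if only women who deliver before Visit 3 lose their dates, given the assumed mixture (10% unresolved, means of 15 and 2.5 days) and the assumed delivery distribution. That percentage covers dropped values only; truncation at Dose 2 is not included. The median is little affected. The primary percentages with each reaction and the maximum severity grades are not affected, because neither uses an end date.

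A reader might take the 16% or 33% scenarios as an estimate of the bias. They are arithmetic limits under losses for which the documents offer no mechanism.

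**What to change.** Change the SAP only.

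- In 3.1.1.1 (and so, by reference, 3.1.1.2 and 3.1.1.3), state that a reaction with no known end date, or ongoing at the next vaccination, is right-censored at the last date it was known to be present. Say whether Vaccination 3 counts as a next vaccination for this purpose.
- In 6.1.1.1.2 and 6.1.1.2.2, report by dose and vaccine group the number of censored reactions, the number and percentage of reactors with a reaction known to last beyond Day 7, and a Kaplan-Meier median beside the planned summary.

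The counts matter most, since they show directly whether the issue is empty or real. The Kaplan-Meier median assumes that censoring is unrelated to the remaining duration, which is why it belongs beside the planned statistics and not in their place.

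The cost is minor programming and a slightly longer supplementary table. No new data are needed. Asking for outstanding stop dates at delivery or the 1-week call is no longer an option. Enrollment ended on 25 Oct 2021; adding 28 days of screening, 42 days to Dose 2, 17 days to Visit 3 and 10 days to the call makes 97 days, or 30 Jan 2022. The SAP version is dated 31 Mar 2022.

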3.1.1.2. Systemic Events (Systemic Event Symptoms and Fever)

The systemic events assessed and recorded in the e-diary are fever, vomiting, diarrhea, headache, fatigue/tiredness, chills, new or worsened muscle pain, and new or worsened joint pain from Day 1 through Day 7, where Day 1 is the day of each dose. The derivations for systemic events will be handled in a way similar to the handling of local reactions with respect to presence of event, severity level, duration, and onset day (see [Section 3.1.1.1](#)).

The symptoms will be assessed by the participant as absent, mild, moderate, or severe according to the grading scale in [Table 5](#).

Table 5. Systemic Event Grading Scale

	Mild (Grade 1)	Moderate (Grade 2)	Severe (Grade 3)	Potentially Life Threatening (Grade 4)
Vomiting	1-2 times in 24 hours.	>2 times in 24 hours.	Requires IV hydration.	Emergency room visit or hospitalization for hypotensive shock.
Diarrhea	2 to 3 loose stools in 24 hours.	4 to 5 loose stools in 24 hours.	6 or more loose stools in 24 hours.	Emergency room visit or hospitalization for severe diarrhea.
Headache	Does not interfere with activity.	Some interference with activity.	Prevents daily routine activity.	Emergency room visit or hospitalization for severe headache.
Fatigue/tiredness	Does not interfere with activity.	Some interference with activity.	Prevents daily routine activity.	Emergency room visit or hospitalization for severe fatigue.
Chills	Does not interfere with activity.	Some interference with activity.	Prevents daily routine activity.	Emergency room visit or hospitalization for severe chills.
New or worsened muscle pain	Does not interfere with activity.	Some interference with activity.	Prevents daily routine activity.	Emergency room visit or hospitalization for severe new or worsened muscle pain.
New or worsened joint pain	Does not interfere with activity.	Some interference with activity.	Prevents daily routine activity.	Emergency room visit or hospitalization for severe new or worsened joint pain.

Abbreviation: IV = intravenous.

Oral temperature will be collected in the evening, daily, for 7 days following each dose (Days 1 through 7, where Day 1 is the day of each dose) and at any time during the 7 days that fever is suspected. Fever is defined as an oral temperature of $\geq 38.0^{\circ}\text{C}$ (100.4°F). The highest temperature for each day will be recorded in the e-diary.

Temperature will be measured and recorded to 1 decimal place. Temperatures recorded in degrees Fahrenheit will be programmatically converted to degrees Celsius for reporting. Temperatures $< 35.0^{\circ}\text{C}$ and $> 42.0^{\circ}\text{C}$ will be excluded from the analysis. Fever will be grouped into ranges for the analysis according to Table 6 below.

Table 6. Scale for Fever

$\geq 38.0^{\circ}\text{C}$ to 38.4°C (100.4°F to 101.1°F)
$> 38.4^{\circ}\text{C}$ to 38.9°C (101.2°F to 102.0°F)
$> 38.9^{\circ}\text{C}$ to 40.0°C (102.1°F to 104.0°F)
$> 40.0^{\circ}\text{C}$ ($> 104.0^{\circ}\text{F}$)

Note: Fever is defined as temperature $\geq 38.0^{\circ}\text{C}$ ($\geq 100.4^{\circ}\text{F}$).

